## Piloting of methods

In Phase 1, we will undertake a feasibility and pilot testing of methods of collecting the information which will form part of the Phase 2 dataset. Much of this could be gathered using a questionnaire format, although some may be extracted from patient information held on the clinical database, or by asking the patient directly in an interview. The most effective and efficient means of gathering the information will be piloted in Phase 1: Patient age, gender, Index of Multiple Deprivation (derived from postcode), patients' education level, household income level and socio-economic classification based on occupation, frequency of dental attendance, payment for dental care, dental experience of a variety of procedures, experience of dental pain and number of natural teeth remaining, risk perceptions (patient perceptions of the likelihood and potential severity of negative oral health outcomes; as well as willingness to pay, and intended, reported and objectively verified (with clinical outcome data) behaviour change.

University of Liverpool researchers (funded by HSDR) will train dental nurses in each of the four dental practices involved in the study to collect this formation as well as gather information on WTP. Piloting will involve taking members of the public and patients, including Patient and Public Involvement members of the project team through the WTP exercise and then discussing the process with them, to understand where improvements could be made.

Phase 1 preparation will also involve training dentists and dental team members to take QLF photographs and for clinical staff to interpret these and give information to patients. Dental team members will also receive training in Good Clinical Practice and study procedures such as: gathering consent for the study, undertaking randomisation procedures and completing study records such as recruitment logs etc. A checklist of the main preventive messages given by dentists to patients at the check-up will be produced for use in all three arms of the experimental study.

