WTP will be elicited using a shuffled payment card method, where a range of values are shown to the patient one at a time in a random order (Smith, 2006). The participant then decides for each value whether they are willing to pay the amount, unwilling to pay it or unsure. This then leaves a range between the lowest value that the participant is unwilling to pay and the highest value that they are willing to pay. The patient will then be asked to name the value between (and including) these values that would be the maximum they would be willing to pay. The decision for each card therefore is similar to a dichotomous choice (as recommended by Arrow and Solow, 1993)), but the whole process finishes with an open ended question. This approach minimises some of the problems associated with using either one of these methods on their own, such as starting point and range bias and making the cognitive task too difficult. Where participants give a zero value, they will be asked to identify the reason for the zero valuation from a range of options presented verbally and on a card. This will allow zeros to be later classified as true zeros or protest responses.

Baseline QLF photographs will then be taken of all patients to measure plaque levels. The patients will then brush their teeth and a second QLF photograph taken to measure tooth mineralisation. At this stage there will be no disclosure of the photograph to patients.

Patients will then have their dental check-up appointment (which will include a BPE examination). The dentist will open the randomisation envelope and patients will then be given their own personal risk information according to the randomisation schedule: either 1) Verbal only information (Model 1) or 2) Verbal information supported by a printed copy of the patients' oral health and risk of disease displayed as a traffic light (Red, Amber or Green), (Model 2) or 3) Verbal information supported by the QLF photographs taken earlier.

In the QLF arm the dentist will discuss the images with the patient in an electronic form on a Tablet PC. These patients will be offered an e mailed electronic image and/or a printed copy of the most meaningful image (either plaque or mineral loss) in a credit card size. A record will be made if an electronic image is sent. In the Traffic Light arm patients will be given a

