credit-card sized information showing their risk level according to colour on the card. In the Verbal only arm patients will receive a plain card with a checklist where the message given by the dentist is written. The reverse of the credit-card sized information from the QLF arm and the Traffic Light arms will have the same checklist (Figure 1):

Figure 1: Checklist of possible preventive messages given to patients

- Stopping or quitting smoking
- Following your dental treatment plan

Following the check-up the dentist or nurse will record as data variables:

- The number of natural teeth present
- Whether the patient is exempt or not from NHS charges
- Any messages given as checked against the Figure 1 list
- The Red, Amber or Green risk rating assigned to patients in the Traffic Light arm

Following the dental appointment, all patients will be given the opportunity to revise their WTP for the information form experienced (therefore this will not be relevant to those in Model 1 who receive only verbal information and they will not undertake this part of the study). For this re-valuation, patients will be reminded of their initial valuation and then asked in a single open-ended question format if they wish to change the value and what amount they would change to.

Self-report data will then be collected at this point on:

- Intention to behave according to the behaviours listed in Figure 1 before the next appointment
- Behaviour change variables as outlined by the Extended Parallel Process Model (EPPM) (Severity of Threat, Susceptibility of Threat, Self-Efficacy and Response Efficacy). The 'threat' here will be the threat of poor oral health and its consequences identified from Phase 1 (for detail see Measures: 5b Risk (threat) perception). An additional set of items will be added to reflect affect concerned with negative oral health outcomes i.e. '*How would you feel if...*' (in addition to the cognition set reflected in EPPM domains).
- Patient-Clinician communication (Communication Assessment Tool, CAT).

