# Visit 2 (V2):

At the second visit (scheduled 2-3 weeks later), but before seeing the dentist or other dental team member, self-reported data will be collected on: self-assessed oral health data and oral health behaviours in the areas listed on the message card (given at the first visit) using an item stem of 'Since my last appointment I have..'. This will be followed by questions oral hygiene, diet and smoking behaviours as repeated measures from Visit 1. A set of EPPM items related to perceived susceptibility to risk of negative oral health outcomes will also be repeated.

A second QLF will be taken for all patients (none of these will be given to patients – they will be used to measure clinical outcomes).

At this appointment dentists or other team members will take another BPE score.

Visit 3 (V3): (scheduled 2-3 weeks after visit 2 (V2)), Self–assessed oral health and selfreported behaviour data collected on V2 will be repeated and a third QLF photograph taken to provide clinical (objectively verified data) on behaviour change.

At this appointment dentists or other team members will take another BPE score.

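### The written checklist is tied to the printed QLF card, which is only one half of an and/or offer, so QLF patients may miss written advice that the other two arms always receive

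*Protocol*

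**What the plan says.** All the delivery rules are in the Protocol, Procedures, Visit 1 (V1).

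- **Verbal arm:** "In the Verbal only arm patients will receive a plain card with a checklist where the message given by the dentist is written". This is unconditional.
- **Traffic Light arm:** "In the Traffic Light arm patients will be given a" card of credit-card size showing the risk colour. This too is unconditional.
- **QLF arm:** "These patients will be offered an e mailed electronic image and/or a printed copy of the most meaningful image", the print being of credit-card size. This is an offer with alternatives.
- **Where the checklist sits:** "The reverse of the credit-card sized information from the QLF arm and the Traffic Light arms will have the same checklist".
- **What is recorded about the QLF item:** "A record will be made if an electronic image is sent". The list of variables completed after the check-up adds the messages given, but not whether a card was handed over.

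Two other sections show what was intended. Piloting of methods says that the checklist "will be produced for use in all three arms of the experimental study". Visit 2 (V2) collects self-reports on "oral health behaviours in the areas listed on the message card (given at the first visit", with no arm excepted.

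**The concern.** The checklist looks like a common element that should reach all arms equally, leaving the form of the risk information as the contrast. In the QLF arm it is attached to the printed image, and the print is optional. Nothing says that the e-mail carries the checklist, or that a patient who takes only the e-mail is given a separate card.

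The patient's own choice of format would then decide who goes without written advice, and only in one arm. Any between-arm comparison of an outcome measured after the check-up could combine the effect of seeing the image with the effect of having, or lacking, a written reminder. That covers intention, the EPPM items, self-reported behaviour, plaque and BPE scores, and possibly the revised WTP after experience.

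**Working it through.** **Step 1: follow the text for each kind of patient.**

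| Patient | Item received under Visit 1 | Written checklist? |
|---|---|---|
| Verbal | Plain card | Yes |
| Traffic Light | Colour card, checklist on reverse | Yes |
| QLF, print only | Image card, checklist on reverse | Yes |
| QLF, print and e-mail | Image card plus e-mail | Yes |
| QLF, e-mail only | E-mail | None stated |
| QLF, declines both | Nothing | None stated |

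The last two rows are permitted by the offer and do not satisfy what Piloting of methods and Visit 2 presuppose. E-mail only is a natural choice, since the Aims describe this arm as an electronic image.

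**Step 2: which outcomes are exposed.** Hypothetical WTP is elicited at Visit 1 before the check-up, and the dentist opens the envelope at the check-up. The primary outcome therefore precedes any card. Intention and the EPPM items follow the check-up, and reported behaviour, plaque and BPE are followed up at V2 and V3, so these can be affected.

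**Step 3: what the record can separate.** With only the sending of an e-mail recorded:

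- E-mail sent: either e-mail only (no card) or e-mail plus print (card). The two cannot be told apart.
- E-mail not sent: either print only (card) or both declined (no card). These too are not distinguished.

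**Step 4: numbers of patients.** There are 133 per arm (Randomisation). The e-mail-only share is not given, so a range is assumed:

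- 10%: 0.10 × 133 = 13.3, about 13
- 25%: 0.25 × 133 = 33.25, about 33
- 50%: 0.50 × 133 = 66.5, about 67

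In the other two arms it would be 0 of 266 (2 × 133).

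**Step 5: an illustration on plaque.** The section on sample size gives an SD of 10 for the plaque percent index (PPI) and 133 per group to detect a difference of 3.5 with 80% power at the 0.05 level, taken here as two-sided.

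- Standard error of the difference = 10 × √(2/133) = 1.226
- Power at 3.5 = Φ(3.5/1.226 − 1.96) = Φ(0.894) = 0.814
- Smallest difference detectable with 80% power = (1.96 + 0.842) × 1.226 = 3.44

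The plan's own figure is reproduced. Now assume that QLF would be better by 3.5 points if everyone had the checklist, and that the written checklist is worth c points. With a share f lacking it, the contrast becomes 3.5 − f × c:

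| f | c = 1: contrast, power | c = 2: contrast, power |
|---|---|---|
| 10% | 3.40, 79% | 3.30, 77% |
| 25% | 3.25, 76% | 3.00, 69% |
| 50% | 3.00, 69% | 2.50, 53% |

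Both f and c are invented. The table shows how the mechanism would act, not how large it is here.

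**The case against.** The best case against is that this is loose wording and not a decision to withhold anything. Piloting of methods wants the checklist in all three arms. The sentence about the reverse of the card carries no condition, and Visit 2 speaks of a card given to patients at the first visit. On that reading the and/or governs only the image format, and a card is always handed over. The Procedures heading also points to a flow diagram and a study crib sheet, which were not available for this review and might settle the matter. Every arm also gets the advice verbally, so the card is only a reminder. At Visit 2 the card merely defines the areas asked about, and a patient can answer without holding it.

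Much of this stands. The intent was probably a card for everyone. However, that intent is not carried into the delivery rule, and practices could follow the rule in different ways.

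A reader might go further, and four stronger readings should be set aside:

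- **That some QLF patients will get no written messages.** The Protocol permits this but does not show that it will happen.
- **That the bias is of known size, for example a fixed share of the 3.5-point PPI difference.** If the card is assumed to be worth the whole 3.5 points, the answer merely restates the assumed e-mail-only share.
- **That the bias runs against the arm of main interest.** The Aims compare three methods without singling one out, and the direction depends on the checklist being helpful.
- **That nothing could be done afterwards.** The sending of e-mails and the messages given are both recorded, so a partial sensitivity analysis is possible. Actual receipt of the card would still be unresolved.

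**Conclusion.** The point holds as an internal inconsistency with a consequence for secondary outcomes. The Visit 1 delivery rule allows a QLF patient to leave without the checklist, while the two other arms always receive it and two other sections take for granted that everyone does. The primary comparison of hypothetical WTP is untouched. Comparisons made after the check-up could mix the image with unequal, self-selected written advice. The size cannot be stated from the Protocol, because it rests on the share taking no print and on the effect of the checklist, and neither is given. The inconsistency is worth correcting before recruitment, because receipt of the card cannot be reconstructed reliably from the data to be recorded.

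**What to change.** In Procedures, Visit 1, state that every patient in the QLF arm receives the checklist card, whether the image is e-mailed, printed, both or neither. Align the flow diagram and crib sheet with that sentence. In the list of variables recorded after the check-up, add which items were given: checklist card, printed image, e-mailed image.

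The cost is one sentence and one set of tick-boxes. Cards are already being produced for the arms. The small drawback is that patients who want only an electronic image will also be given a paper card.

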## Procedures (see Flow diagram and Study Crib sheet)

# Visit 1 (V1):

Before their dental check-up, for patients recruited to the study a measure of the patients' literacy (REALM) will be administered by a dental nurse. The following data will then be gathered as self-reports: demographic (age, gender, income, education, employment status); psycho-graphic (previous experience of dental care, self-rated oral health, dental anxiety (MDAS); and oral health behaviours (diet, oral hygiene and smoking).

Information on patients' hypothetical incremental Willingness to Pay (WTP) for both the Traffic Light and QLF information systems (using Verbal information only as a base line for comparison), will be gathered. The systems will be explained hypothetically using written and visual information giving a generalised description of that type of information, but without reference to the patients' personal oral health status/risk. Following an outline of the 3 scenarios, patients will first be asked which of the forms of information is preferred including the current practice of Verbal information only (ranking) and then incremental WTP will be elicited for traffic light and QLF both compared to Verbal only (i.e. what extra would some be willing to pay (if at all) to receive either traffic light or QLF over verbal information only) in this face to face setting.

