## Phase 2 Analysis

# WTP

We will compare hypothetical Willingness to Pay for each of the information systems across the whole sample (primary outcome) across the 3 arms. We will also compare hypothetical WTP with WTP for a good that has been "consumed" by comparing WTP before and after receiving the information. WTP data will be analysed both descriptively, comparatively and econometrically. Descriptive data analysis will consist of WTP value means with standard deviations along with medians and quartiles for each information system. The WTP values for each system will be compared using appropriate comparative tests (e.g. most likely to be Mann Whitney U tests given the likely distribution).

In order to understand fully how the dental and demographic factors influenced values (WTP), econometric regression analyses will be carried out. A regression model of individual co-variates on WTP will be specified. The regression method will be dependent on the data but is likely to be either OLS or Tobit regression analyses. Tobit models have been recommended for analysis of WTP data because of the censoring of the data at zero (Halstead et al., 1991). The Ramsey RESET test will be used to test for model specification. Individual Tobit models will be constructed for each information system.

Finally, hypothetical WTP data for each information form will be compared to WTP following experience again using the most appropriate comparative tests.

Probable hypothesis tests to be used to compare WTP for different arms and also at different time points and econometric analysis plans to analyse factors that influence WTP. The Ramsey RESET test (Ramsey, 1969) will be used to test for model misspecification. The RESET test tests for omitted variables, incorrect functional form and correlation between independent variables and the error term. Sensitivity analysis using alternative regression analysis (e.g. tobit, OLS Interval regression analysis) will be performed to test whether the results are sensitive to model specification.

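### The before/after WTP comparison is an uncontrolled within-arm change: the Verbal arm, which valued both forms beforehand, is not re-asked

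*Protocol*

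**What the plan says.** Under Procedures, Visit 1 (V1), every patient gives a first valuation before the check-up: "incremental WTP will be elicited for traffic light and QLF both compared to Verbal only". The method is stated as "WTP will be elicited using a shuffled payment card method", and after the cards "the whole process finishes with an open ended question", in which the patient names a maximum within the range the cards have left. The dentist opens the randomisation envelope later, at the check-up. Patients who go on to the Verbal arm therefore already hold first values for both Traffic Light and QLF.

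After the check-up, "all patients will be given the opportunity to revise their WTP for the information form experienced". The same sentence removes the Verbal arm: "this will not be relevant to those in Model 1 who receive only verbal information", and "they will not undertake this part of the study". In the other two arms, "patients will be reminded of their initial valuation and then asked in a single open-ended question format if they wish to change the value".

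Under Phase 2 Analysis, WTP, the protocol sets hypothetical value against the value of a good that has been used. It says that "hypothetical WTP data for each information form will be compared to WTP following experience", with the test left open. It names no comparison arm, no re-valuation of a form not received, and no allowance for re-asking.

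**The concern.** A within-patient change supports a statement about experience only if nothing else that could move the answer happens between the two questions. Here several things happen:

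- The patient is asked a second time.
- The patient is told the first answer, which invites leaving it alone.
- The card step is not repeated.
- The patient has by then had an examination and personal verbal advice, as has every patient in all three arms.

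The protocol defends the combined card and open-ended method partly because it limits starting-point bias. The re-valuation then supplies a starting point, namely the patient's own earlier figure.

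At stake is whether hypothetical values hold up once the form has been used. A finding of no change could reflect the reminder and give false reassurance. A non-zero change could come from re-asking or from the check-up and be credited to the form. The trial has a randomised arm that could separate much of this, but the data are not collected, and no later analysis plan can recover answers that were never asked for.

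**Working it through.** **What each arm contributes**

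| | Verbal | Traffic Light | QLF |
|---|---|---|---|
| First value, Traffic Light and QLF | yes | yes | yes |
| Check-up and verbal advice | yes | yes | yes |
| Second value, Traffic Light | no | yes | no |
| Second value, QLF | no | no | yes |

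No form is re-valued in more than one arm. Setting change in the Traffic Light arm against change in the QLF arm is not planned and would not control for re-asking, because each arm re-values a different good.

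**The plan's own figures.** The protocol states no size or power for the before/after comparison. Its one calculated figure, under Sample size calculation, concerns plaque: 133 per group, SD 10, difference 3.5, 80% power, 0.05. With a two-sided test, the detectable difference is 2.80 × 10 × √(2/133) = 3.44 and the power at 3.5 is 81.4%. This agrees with the protocol. Only the 133 per arm is carried forward.

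**Illustration.** The assumptions are mine: 133 complete pairs per arm, two-sided 0.05, normal approximation, no true effect of experience, and a re-asking shift b in units of the SD of the change score. The SE of the mean change is 1/√133 = 0.0867 SD. The probability that the uncontrolled test is significant is 1 − Φ(1.96 − b√133) + Φ(−1.96 − b√133).

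| Shift b (SD) | b√133 | Significant with no effect of experience |
|---|---|---|
| 0 | 0 | 5% |
| 0.08 | 0.92 | about 15% |
| 0.1 | 1.15 | 21% |
| 0.2 | 2.31 | 64% |
| 0.3 | 3.46 | 93% |

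To give 0.08 SD a concrete meaning: if 20% of patients moved by £2 in the same direction, the mean would shift by 0.20 × £2 = £0.40. With an SD of change of £5, that is 0.40/5 = 0.08 SD. All three inputs are assumed.

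**Price of a control.** Detectable difference at 80% power:

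- paired, within one arm: 2.80/√133 = 0.24 SD
- change in one arm minus change in the Verbal arm, 133 against 133: 2.80 × √(2/133) = 0.34 SD

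A shift common to both arms cancels in the second contrast.

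**The case against.** The other side has real points.

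- **The format switch is partial.** A reader might infer that a card method is replaced by a wholly different question. The protocol does not support that: the first elicitation also ends open-ended. What differs is that the cards are not repeated and the first answer is quoted. This stands.
- **The second question invites a revision.** Leaving the value unchanged is the easy answer, so anchoring tends to make a reported change conservative. This stands for anchoring. It does not cover the check-up and verbal advice, which could move values either way, and it makes a null result harder to read.
- **The protocol makes no explicit causal claim.** It compares a hypothetical value with the value of a used good. That is fair, but the comparison is of interest only if the difference says something about use.
- **The Verbal arm is not an exact control.** A reader might infer that it would isolate the nuisance effects precisely. It would not: these patients would re-value forms they did not receive, and missing out may itself change the answer. Nor would subtraction restore a true effect that the reminder suppresses. It is a close control.
- **The control costs precision.** In the £5 example, the within-arm SE is 5/√133 = £0.43. With a £0.40 bias, the root mean squared error is √(0.43² + 0.40²) = £0.59, against an SE of £0.61 for the unadjusted contrast. At so small a shift the control gains nothing in overall error. Under equal SDs the balance turns at b = 1/√133 = 0.087 SD. This stands, and it is why the size must be left open.
- **Verbal is the baseline, so there is nothing to re-value.** This explains why Verbal is not re-valued. It does not explain why these patients are not re-asked about the two forms they had already valued.

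**Conclusion.** The point holds as a limitation of an additional comparison, and it should be mended at data collection. As designed, the before/after change cannot be separated from re-asking, anchoring, and the check-up with its verbal advice.

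A reader might infer that the primary WTP result is compromised. It is not: the primary hypothetical values are collected from the whole sample before allocation is revealed. A reader might also infer a known bias in pounds. The protocol gives neither an SD nor a shift for WTP change, so none can be stated. The rejection rates of about 15% to 93% rest on assumed shifts of 0.08 to 0.3 SD, complete data on 133 per arm, and a normal approximation. The protocol expects WTP to be skewed, so they show how sensitive the test is and do not predict its behaviour in this trial.

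**What to change.** After the check-up, put the same reminder and revision question, on both Traffic Light and QLF, to Verbal-arm patients as well. Estimate the effect of experience as change in the form received minus change in the same form in the Verbal arm: Traffic Light arm against Verbal for Traffic Light, QLF arm against Verbal for QLF. Adjust for the first value, or use a rank-based method if the changes are skewed. Report the within-arm changes as descriptive, and say that they include re-asking and the check-up.

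The cost is a short extra question for Verbal-arm patients, who already complete questionnaires at that point in a full visit. The contrast is less precise than the paired test, and the control is close without being exact. If the question cannot be added, the least change is to label the before/after comparison descriptive and not attribute it to experience of the form.
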